3.3.2 Secondary endpoints

1. Description of the demographic and clinical profile of patients at the time of treatment initiation (for mCRC)
2. PFS, defined as the length of time between initiation of first-line treatment for mCRC and the first documented disease progression (if disease progression is not well documented in a patient's medical record, then the start of the subsequent LOT may be considered as proxy for disease progression) or death (whichever is earlier)
3. OS, defined as the length of time between first-line treatment initiation (for mCRC) and death (due to any cause)
4. ORR, defined as complete response (CR) or partial response (PR), described at the end of first-line treatment for mCRC
5. Time to treatment cessation, defined as the length of time between initiation of firstline treatment for mCRC and documented disease progression (or start of subsequent LOT, if disease progression is not well documented in the patient medical record), treatment discontinuation or switch to another treatment (defined as change from 1 treatment regimen to another treatment regimen, e.g. change from FOLFOX-based regimen to FOLFIRI or irinotecan-based regimen)
6. Time to BRAF mutation testing since mCRC diagnosis and since first-line treatment for mCRC, and description of testing procedures
7. Frequency of relevant AEs during first-line treatment for mCRC. Relevant AEs are defined as AEs leading to first-line treatment switch, dose adaptation or discontinuation, or leading to death.

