Relevant Adverse events	
 Time to treatment cessation is defined as the length of time between initiation of first-line treatment and documented disease progression (or start of subsequent LOT, if disease progression is not well documented in patient medical record), treatment discontinuation or switch to another treatment (defined as change from 1 treatment regimen to another). Time to treatment cessation will be calculated from the date of initiation of LOT to the date of disease progression, treatment discontinuation or switch. Patients with no disease progression, treatment discontinuation or switch to another treatment will be censored at the earliest of: date of last medical record entry, last day of the observation period or date of death.
Cause of death (for deceased patients)	
 Information on relevant AEs during the study period will be collected based on information available in the patient medical records. Relevant AEs will be mapped into the (MedDRA) and grouped by SOC and PT. 
Relevant AEs are defined as AEs leading to first-line treatment switch, dose adaptation or discontinuation, or leading to death.

Reasons for treatment discontinuation or switch	
 The primary cause of death will be recorded as available in the medical record (cancer-related, non-cancer related, unknown/missing). Reasons for treatment alteration, defined as treatment interruptions, switches and discontinuation, will be collected at the end of each treatment, based on information available in the patient medical records.

¹ For patients in whom disease progression is not well documented, the start date of subsequent LOT will be considered instead of the date of disease progression. Detailed derivation of LOT will be provided in the SAP.

CR: complete response; ICD-10: International Classification of Diseases 10th Revision; mCRC: metastatic colorectal cancer; MedDRA: Medical Dictionary for Regulatory Activities; LOT: line of therapy; ORR: overall response rate; OS: overall survival; PD: progressive disease; PFS: progression free survival; PR: partial response; PT: preferred term; SOC: system organ class.

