3.8.3 Secondary analyses

- **Demographic and clinical profile**

Demographics and baseline clinical characteristics of patients (as outlined in Table 3) will be summarized using descriptive statistics.

- **Progression free survival**

Progression free survival is defined in Table 2. This will be assessed for first-line treatments and described graphically by Kaplan-Meier (KM) survival curves. Median PFS, 25th and 75th percentiles, and corresponding 95% CI will be reported. Cox regression analysis may be performed to adjust for predefined (baseline) covariates and HR and 95% CIs reported.

- **Overall survival**

Overall survival is defined in Table 2. This will be described graphically by KM survival curves and median OS, 25th and 75th percentiles, and correspondent 95% CI reported. Cox regression analysis may be performed to adjust for predefined (baseline) covariates; HRs and 95% CIs will be reported.

- **Treatment response**

The category of objective response following treatment (CR, PR, and PD) will be summarized by first-line SACT treatments (monotherapy, doublet therapy, triplet therapy) and by treatment regimens using frequency tables with their associated 95% CIs. Additionally, ORR is defined in Table 2. Logistic regression may be used to adjust for predefined (baseline) covariates; odds ratios with 95% CIs will be reported.

- **Treatment duration (time to treatment cessation)**

Time to treatment cessation (defined in Table 2) will be assessed for first-line SACT treatments. This will be described graphically by KM survival curves. Cox regression may be used to adjust for predefined (baseline) covariates; HRs and 95% CIs will be reported.

- **BRAF Mutation testing**

Time from metastatic diagnosis to BRAF mutation testing will be assessed in addition to the time from testing to first-line treatment, and all testing procedures will be summarized using descriptive statistics.

- **Safety analyses**

The number and percentage of patients who have at least one of the relevant AE during first-line treatment will be summarized. Clopper-Pearson (Exact) 95% CIs for the proportion will be constructed around the point estimate of the incidence. Tables with counts and frequencies of relevant AEs will be provided and summarized by MedDRA SOC and PT.

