3.8.4 Exploratory analyses

- **Reason(s) for treatment alteration**

The reasons for treatment alteration (dose change, interruptions, switches, discontinuation), as recorded in patient medical records, will be described using descriptive statistics.

- **Treatment patterns for second (and subsequent) LOT**

Second- (and subsequent-) line treatment patterns, in the subset of patients who progress beyond first-line treatment, will be analyzed based on the methods described in primary analysis (Section 3.8.2).

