5.2 REPORTING OF ADVERSE EVENTS/ADVERSE DRUG REACTIONS

5.2.1 Definitions

Adverse event (AE); synonym: Adverse experience

Any untoward medical occurrence in a patient or clinical trial subject administered a medicinal product and which does not necessarily have a causal relationship with this treatment [Dir 2001/20/EC Art 2(m)].

An AE can, therefore, be any unfavorable and unintended sign (e.g., an abnormal laboratory finding), symptom or disease temporally associated with the use of a medicinal product, whether or not considered related to the medicinal product.

Adverse reaction; synonyms: ADR, suspected adverse (drug) reaction, adverse effect, undesirable effect

A response to a medicinal product which is noxious and unintended [DIR 2001/83/EC Art 1(11)].

Response in this context means that a causal relationship between a medicinal product and an AE is at least a reasonable possibility. An adverse reaction, in contrast to an adverse event, is characterized by the fact that a causal relationship between a medicinal product and an occurrence is suspected. For regulatory reporting purposes, if an event is spontaneously reported, even if the relationship is unknown or unstated by the healthcare professional or consumer as primary source, it meets the definition of an adverse reaction. Therefore, all spontaneous reports notified by healthcare professionals or consumers are considered suspected adverse reactions, since they convey the suspicions of the primary sources, unless the primary source specifically state that they believe the event to be unrelated or that a causal relationship can be excluded.

Adverse reactions may arise from use of the product within or outside the terms of the marketing authorization or from occupational exposure [DIR 2001/83/EC Art 101(1)]. Use outside the marketing authorization includes off label use, overdose, misuse, abuse and medication errors.

Serious adverse reaction

An adverse reaction which results in death, is life-threatening, requires in-patient hospitalization or prolongation of existing hospitalization, results in persistent or significant disability or incapacity, or is a congenital anomaly/birth defect is considered a serious adverse reaction [DIR 2001/83/EC Art 1(12)].

Life-threatening in this context refers to a reaction in which the patient was at risk of death at the time of the reaction; it does not refer to a reaction that hypothetically might have caused death if more severe (ICH-E2D Guideline).

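### The relevant-AE rule neither excludes progression or death from mCRC nor lists treatment interruption, so the by-regimen AE frequency cannot be read as regimen toxicity

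*Combined protocol and SAP*

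**What the plan says.** The rule for endpoint 7 is the same in the synopsis, Section 2.2, Section 3.3.2 and Table 2: "Relevant AEs are defined as AEs leading to first-line treatment switch, dose adaptation or discontinuation, or leading to death". It has four triggers: switch, dose adaptation, discontinuation and death.

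The protocol defines an AE only in Section 5.2.1: "Any untoward medical occurrence in a patient or clinical trial subject administered a medicinal product", with the qualifier "which does not necessarily have a causal relationship with this treatment". The scope extends to any "symptom or disease temporally associated with the use of a medicinal product, whether or not considered related to the medicinal product". Progression is neither named nor excluded.

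Table 2 lists interruption as a treatment alteration: "Reasons for treatment alteration, defined as treatment interruptions, switches and discontinuation, will be collected at the end of each treatment". The exploratory analysis in Section 3.8.4 does too, and keeps it apart from dose change: "The reasons for treatment alteration (dose change, interruptions, switches, discontinuation), as recorded in patient medical records".

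The planned safety output in Section 3.8.3 is a crude share: "The number and percentage of patients who have at least one of the relevant AE during first-line treatment will be summarized". It comes with an exact 95% CI and tables by SOC and PT. Section 2.2 asks for the frequency overall and by treatment regimen.

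**The concern.** Chart abstractors at up to 65 sites have to decide what counts as a relevant AE. When first line is stopped because the tumour has grown, or the patient dies of mCRC on first line, one abstractor may enter an AE and another only a progression date or cause of death. The text supports either choice. The reported percentage would then depend partly on site habit, and more so for regimens given to patients with a poorer prognosis.

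Interruption pulls the other way. Toxicity handled only by holding or delaying treatment fits none of the four triggers as written, so a regimen usually managed that way would appear better tolerated.

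A third problem lies in the output. A crude percentage grows with time on treatment, and that time may differ between regimens.

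The study is meant to describe the safety of current regimens, to put the single-arm ANCHOR trial into context, and possibly to support health technology assessment (study rationale). Readers will take the by-regimen AE figure as a statement about toxicity.

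**Working it through.** The plan gives no expected AE frequency, so there is no figure of its own to reproduce. The check compares the texts and then illustrates scale.

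**1. Progression and cancer death.**
- Section 5.2.1 requires no relatedness.
- Endpoint 7 adds only the four triggers.
- Section 3.8.3 applies no filter for relatedness or progression, and no collection of relatedness or grade is described.
- Table 1 collects the progression date and Table 2 the cause of death (cancer-related, not cancer-related, unknown). Neither is linked to the AE rule.

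The text therefore does not settle whether these events count.

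**2. Interruption.**

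| Place | Alterations named |
|---|---|
| Endpoint 7 triggers | switch, dose adaptation, discontinuation (plus death) |
| Table 1 (examples) | switch, discontinuation, dose escalation or reduction |
| Table 2 | interruption, switch, discontinuation |
| Section 3.8.4 | dose change, interruption, switch, discontinuation |

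Dose adaptation is never defined. Since Section 3.8.4 separates interruption from dose change, the natural match for dose adaptation is dose change.

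**3. AE window.** It is the follow-up period in the synopsis, the study period in Table 2, and first-line treatment only in Section 3.3.2, Table 4 (footnote 8) and Section 3.8.3. Under the wider windows, deaths in later lines could count.

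**4. Scale of inconsistent entry.** Let T be the share with a toxicity-type relevant AE and q the share with progression or cancer death entered as an AE. Neither is in the documents. If the two are independent, the reported share is 1 − (1 − T)(1 − q). With T = 30%:
- q = 5%: 1 − 0.70 × 0.95 = 33.5%
- q = 10%: 1 − 0.70 × 0.90 = 37.0%
- q = 25%: 1 − 0.70 × 0.75 = 47.5%
- q = 50%: 1 − 0.70 × 0.50 = 65.0%

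For other T, with the same four values of q: T = 20% gives 24%, 28%, 40% and 60%; T = 40% gives 43%, 46%, 55% and 70%.

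Without independence, the share lies between max(T, q) and T + q. For T = 30% and q = 10%, that is 30% to 40%.

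For comparison, the exact 95% CI for 90 of 300 patients is 24.9% to 35.5%. Under independence the reported share passes the upper limit once q exceeds (0.355 − 0.30)/0.70, about 8%. In a single regimen the sampling error is wider: for 18 of 60 patients (a regimen given to 20% of 300) the interval is 18.8% to 43.2%, so a shift to 37% stays inside it. The bias does not shrink with sample size.

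**5. Scale of exposure.** At an assumed constant hazard of 5% per month, the crude percentage is 1 − exp(−0.05 × 3) = 13.9% after 3 months on treatment and 1 − exp(−0.05 × 9) = 36.2% after 9. The hazard and the durations are illustrative.

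**The case against.** The strongest reply is that the protocol never calls progression or cancer death an AE. It gives each its own field, and also collects reasons for discontinuation or switch. The general AE definition sits in the pharmacovigilance section and is not stated to be the abstraction rule for endpoint 7. First line ends at documented progression (Section 3.3.4), which limits how far progression can enter a first-line window. This stands against a stronger reading that a reader might infer: that the rule includes progression and that most patients would therefore have a relevant AE. Assuming T = 30% and that 60% to 75% of patients end first line through progression or cancer death, full entry would give 1 − 0.70 × 0.40 = 72% to 1 − 0.70 × 0.25 = 82.5%. That needs every site to enter every such event, uses inputs found nowhere in the documents, and treats as independent two causes that compete to end first line.

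Dose adaptation could also be read to cover a held or delayed dose. Interruptions and their reasons are described in Section 3.8.4, so that information is not lost to the study. This makes the omission a matter of literal reading, but it leaves the choice to each site.

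Treatment duration is reported separately and the study tests no hypothesis, so a crude frequency is a legitimate description. A rate is still needed before regimens can be read side by side.

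Finally, Section 3.11.2 promises clear definitions and eCRF guidelines, and the SAP, whose text is not part of the document reviewed, is still to come. An analysis rule could remove terms coded as progression, which would show in the PT tables. It could not reliably separate tumour symptoms from toxicity, nor restore interruption-only toxicity that was never entered as an AE. The SAP is due only before database lock (November 2020), whereas data entry starts in April 2020. The site enrollment record is destroyed at lock (Section 3.7), so charts cannot be re-queried afterwards.

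**Conclusion.** The concern holds as a gap in the definition. The rule does not exclude progression of mCRC or death from it, does not name interruption, and is tied to three different windows. The resulting by-regimen frequency cannot be read as regimen toxicity.

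It would go too far to say that the endpoint does not measure toxicity at all. Its stated target is the frequency of relevant AEs, and it still captures toxicity that leads to switch, dose adaptation, discontinuation or death.

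The size is unknown because the rate at which sites would enter progression is unknown. With an assumed 30% toxicity-type share and independence, entry for 5% to 50% of patients gives about 34% to 65%. At 5% the shift is within sampling error for 300 patients; at 10% it is not. The documents give no basis for a figure on interruption-only toxicity. The endpoint is secondary and descriptive, so this is a worthwhile low-cost correction and does not threaten the primary objective.

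**What to change.** Make these changes in Table 2 and the eCRF completion guideline before data entry, and carry the wording to the synopsis and Sections 2.2 and 3.3.2:

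1. State that progression of mCRC and death due to mCRC are not counted as relevant AEs and are reported under PFS and cause of death. Cross-check every fatal AE against the cause-of-death field.
2. Define dose adaptation, and add AEs leading to interruption or delay to the triggers, in line with Table 2 and Section 3.8.4.
3. Beside each crude by-regimen percentage, give first relevant AEs per 100 patient-months on first-line treatment. Table 1 already collects treatment start and stop dates and alteration dates.
4. Reconcile the AE window across the synopsis, Table 2, Section 3.3.2, Table 4 and Section 3.8.3.

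The cost is definition and guideline wording, slightly more AE entry for interruptions, and one extra table column.

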3.3.3 Exploratory endpoints

1. Description of reasons for treatment discontinuation or switch at the end of first-line treatment for mCRC
2. Second (and subsequent) line treatment patterns in BRAF^{V600E} mutant mCRC patients, defined as treatments received after disease progression following first-line treatment, and described by:
 - Agent or combination of agents received
 - Duration of treatment

3.3.4 Exposure definition and measurement

This is a NIS of real-world treatment practices in the adult BRAF^{V600E} mutant mCRC patient population. This protocol does not recommend the use of any specific treatments, and no study medication will be provided as part of participation in the study.

The exposure of interest will be the first-line SACT (monotherapy, doublet therapy, or triplet therapy with or without a targeted therapy [either VEGF inhibitor or EGFR inhibitor]) for the treatment of BRAF^{V600E} mutant mCRC. Treatment patterns will be described by LOT.

Line of therapy will be defined as follows:

- First LOT: the start of first LOT will be defined as the first administration of SACT therapy after diagnosis of mCRC to the date of first documented disease progression
- Second and subsequent LOTs: mCRC treatment(s) received on or after the date of documented disease progression following previous LOT to the date of documented disease progression on or after the current LOT
- In the absence of information on disease progression, an algorithm will be specified in the SAP based on the specific treatment(s) received (stop and start dates), progression (as recorded in the patient medical record, including date), documented reasons for discontinuation of treatments and gap(s) between subsequent treatment regimens.

The exposure variables of interest are described in Table 1.

Table 1 Study Exposure

Exposure	Definition and Measurements
Systemic anti-cancer therapy (SACT) ¹ for mCRC	
 Details on SACT (by LOT) 
 LOT² (e.g., first, second, third, etc.) Type of treatment³ (i.e., monotherapy, doublet therapy, triplet therapy) Agents used 
 Chemotherapy regimens (e.g., FOLFOX, FOLFIRI, FOLFOXIRI) Targeted agents (e.g., bvacizumab, cetuximab, panitumumab) Duration of treatment: start date and stop date Date of documented progression Dates and reasons for treatment alteration (e.g., switch, discontinuation, dose escalation/reduction) Maintenance therapy (if any) of first line treatment: name of agent(s); start date and stop date Treatment response (as recorded in patient medical record by the treating physician) of first-line treatment of mCRC: type of response (CR, PR, PD); date recorded

¹ All SACT treatments received/prescribed for mCRC will be captured.

² LOT will be defined algorithmically, using a data-driven approach if disease progression is not well documented in the patient medical record. Details will be specified in the SAP.

³ This will be a derived field, based on the SACT treatments received/prescribed.

CR: complete response; FOLFOX: 5-fluorouracil (5-FU), leucovorin, and oxaliplatin; FOLFIRI: 5-FU, leucovorin, and irinotecan; FOLFOXIRI: 5-FU, leucovorin, oxaliplatin, irinotecan; LOT: line of therapy; mCRC: metastatic colorectal cancer; PD: progressive disease; PR: partial response; SACT: systemic anti-cancer therapy

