First-line treatment in patients with mCRC includes a combination of chemotherapy regimens and biological agents.^{3 4} Systemic anti-cancer therapy (SACT) is the main treatment option where combination chemotherapy remains the consensus standard of care. Current guidelines advocate the doublet combinations with oxaliplatin (5-fluorouracil [5-FU], leucovorin, and oxaliplatin [FOLFOX]) or irinotecan (5-FU, leucovorin, and irinotecan [FOLFIRI]) based regimens.² These regimens are shown to be superior to combination of 5-FU and folinic acid alone.²⁴

Targeted therapy, including vascular endothelial growth factor (VEGF) inhibitor bevacizumab or epidermal growth factor receptor (EGFR) monoclonal antibodies (cetuximab and panitumumab), is currently recommended by clinical guidelines as selective addition to the chemotherapy regimens, taking into account patient's RAS status.² Bevacizumab, when given in combination with chemotherapy has shown to significantly improve overall survival (OS) compared to chemotherapy alone.^{5 6} The survival benefit was retained in patients who continued using bevacizumab as a combination therapy, beyond first-line progression.⁷ Other biological agents such as cetuximab and panitumumab, both of which are EGFR monoclonal antibodies, have demonstrated benefits in survival, progression free survival (PFS) and response rate when used as first-line treatment of patients with wild-type KRAS (KRASwt) tumors in combination with FOLFIRI and FOLFOX when compared to chemotherapy alone, but not with other oxaliplatin-based regimens such as FLOX

(combination of fluorouracil, leucovorin and oxaliplatin) and CAPOX (combination of capecitabine and oxaliplatin).³⁻⁸

B-Raf proto-oncogene mutant colorectal cancer

BRAF encodes a serine/threonine protein kinase belonging to the RAS/RAF/mitogen activated protein kinase (MEK)/extracellular signal-regulated kinase (ERK) kinase pathway that has been implicated in pathophysiology proliferation, invasion, and metastasis in CRC.²⁵ Approximately 5% to 15% of CRC patients have a mutation in the BRAF gene resulting in a valine-to-glutamate change at the residue 600 (V600E), which is nearly always mutually exclusive with the RAS mutation.^{6-9,26}²⁷ Multiple clinical trials suggest that BRAF mutation is a poor prognostic factor for mCRC.^{10,12,28,29}

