3.3 STUDY OUTCOMES

3.3.1 Primary endpoint

The primary endpoints are first-line SACT treatment patterns in BRAF^{V600E} mutant mCRC patients, described by:

- Agent or combination of agents received
- Duration of treatment
- Maintenance therapy (if any)

The first-line SACT regimen(s) will be described from the time of treatment initiation (for mCRC) until the time of first documented disease progression, treatment discontinuation or switch, whichever is earlier.

LOT definition will be connected to treatment progression. The LOT will be defined using a data-driven approach. In the SAP an algorithm for LOT definition will be specified, which will consider the specific treatment(s) received (stop and start dates), progression (as recorded in the patient medical record, including date), documented reasons for discontinuation of treatments and gap(s) between subsequent treatment regimens.

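### With documented progression, the line-of-treatment rule in Section 3.3.4 counts first-line or maintenance treatment that merely continues as second line

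*Combined protocol and SAP*

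**What the plan says.** Section 3.3.4 defines the first LOT as running from "the first administration of SACT therapy after diagnosis of mCRC to the date of first documented disease progression". Second and later LOTs are "mCRC treatment(s) received on or after the date of documented disease progression following previous LOT", up to the next documented progression. The criterion is that treatment was received. Neither definition mentions a new agent, a changed regimen or a new start date.

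Section 3.3.3 defines the second-line exploratory endpoint by a similar date rule, "defined as treatments received after disease progression following first-line treatment", which leaves out the day of progression itself. Section 3.8.4 analyses second and later lines "in the subset of patients who progress beyond first-line treatment" and adds no condition on the treatment.

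On the algorithm promised for the SAP, the sections differ:

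- Section 3.3.4, third bullet: "In the absence of information on disease progression, an algorithm will be specified in the SAP".
- Table 1, footnote 2: "LOT will be defined algorithmically, using a data-driven approach if disease progression is not well documented in the patient medical record".
- Section 3.3.1, with no such limit: "In the SAP an algorithm for LOT definition will be specified, which will consider the specific treatment(s) received (stop and start dates". The endpoint section of the synopsis is also unrestricted.

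The supplied text does not contain the algorithm.

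**The concern.** For patients with a documented progression date, the calendar alone separates the lines. A patient may receive a cycle of the old regimen on the day progression is recorded, or stay on maintenance for a while before the change. By the wording of Section 3.3.4 that patient is already in second line. Any new regimen given afterwards, before the next progression, falls into the same line.

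The situation is foreseeable. The background notes of bevacizumab that "The survival benefit was retained in patients who continued using bevacizumab as a combination therapy, beyond first-line progression". That sentence concerns one agent, not an unchanged regimen, but it shows that treatment does not always stop at progression.

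Exploratory objective 2, the treatments received by line after first progression, is at stake. Patients who only continued old treatment would count as treated in second line, old regimens would appear among second-line choices, and second line would start too early.

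**Working it through.** **The plan's own figure.** The only design figure is the precision in Section 3.5. The half-width 1.96 × √(p(1 − p)/300) gives 2.47, 3.39 and 4.53 points at p = 5%, 10% and 20%, in agreement with Table 5. It concerns regimen shares in first line and plays no part below. This point is about a definition.

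**Step 1: the rules side by side, progression documented.**

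| Place | What it sets | New or changed regimen required? |
|---|---|---|
| 3.3.4, first bullet | LOT 1 runs to the progression date | Not applicable |
| 3.3.4, second bullet | LOT 2 holds treatment received from the progression date on | No |
| 3.3.3 | Second line holds treatment received after progression | No |
| 3.3.1 | First-line description ends at the earliest of progression, discontinuation or switch | Not applicable |
| 3.3.2, item 5 | Defines a switch as a change of regimen, for time to treatment cessation | The LOT rule does not use it |
| Table 1 | Maintenance belongs to first line, with its own stop date | No rule if that date is after progression |

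The progression date falls in both LOT 1 and LOT 2 under 3.3.4, and outside second line under 3.3.3. Maintenance that stops after progression is first line under Table 1 and, for its later part, second line under 3.3.4.

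**Step 2: the literal rule on a hypothetical patient.** Progression is documented on day 180.

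| Day | Treatment | Line under 3.3.4 |
|---|---|---|
| 0, 14 | First-line doublet | 1 |
| 120 | Maintenance | 1 |
| 180 | Same maintenance | 2 (day 180 is also the end of LOT 1) |
| 194 | Same maintenance | 2 |
| 230 | New regimen | 2 |

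Second line opens on day 180 with unchanged maintenance. The first new treatment is on day 230, 50 days later.

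**Step 3: how large it could be.** The documents do not say how often treatment continues past progression, so all three inputs are assumptions:

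- P, patients of the 300 with documented progression: 200 to 280
- q, the fraction of them starting a truly new regimen: 0.50 to 0.70
- f, the fraction with old treatment on or after the progression date, independent of q: 0.05 to 0.20

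Patients with an old regimen in second line = P × f.
Patients counted as second line = P × q + P × f × (1 − q).
Affected share = f / (q + f(1 − q)), which does not depend on P.

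- Low end (P = 200, q = 0.70, f = 0.05): 200 × 0.05 = 10 patients; counted 140 + 3 = 143; share 10/143 = 7.0%.
- High end (P = 280, q = 0.50, f = 0.20): 280 × 0.20 = 56 patients; counted 140 + 28 = 168; share 56/168 = 33.3%.

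Of these, 3 and 28 patients respectively had no new regimen at all and inflate the number treated. The other 7 and 28 have a second line that starts too early.

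**Step 4: endpoints not touched.** In Table 2, OS runs from first-line initiation to death. PFS, where progression is documented, runs to progression or death. Neither uses the start of LOT 2. PFS with the next LOT as proxy applies only where progression is not well documented, and there this rule does not operate.

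**The case against.** The strongest reply is that the plan leaves this to the SAP. The synopsis and Section 3.3.1 promise an algorithm for all patients, using start and stop dates, reasons for discontinuation and gaps. Even the restricted bullet in 3.3.4 lists recorded progression among the inputs, which fits poorly with an algorithm meant only for missing progression. The SAP is due before database lock (Section 3.8.1). A reader might infer from 3.3.4 alone that the algorithm cannot help these patients; the documents do not support that, because they conflict on its scope and do not show its content. Equally, an unwritten algorithm is no cure for a written rule.

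Four further objections stand:

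- Collection is by agent or regimen with start and stop dates (Tables 1 and 4), and no date for each dose is listed. Maintenance is labelled as first line. That every dose after progression would be tabulated as second line is therefore a literal reading, not an established output.
- Table 1 measures duration by the treatment's own start and stop dates. A reader might infer that second-line duration must be too long, but that is only possible.
- Bevacizumab continued with new chemotherapy belongs in second line, and the present rule puts it there.
- The endpoint is exploratory, the study is descriptive, and tying lines to progression is a declared choice.

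It is also tempting to set the affected share against the 1% to 21% in Section 3.5. Those are shares of single regimens in first line, so the comparison is not like for like.

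**Conclusion.** The point holds in a limited form. For patients with documented progression, Section 3.3.4 as written classes treatment that merely continues as the next line. It also puts the progression date in two lines and differs from 3.3.3 on that date. The number treated, the agents and the start date in the second-line tables are open to misclassification, and duration possibly so.

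The size is not known. The range of 10 to 56 patients (about 7% to 33% of those counted as second line) rests wholly on the assumptions in the working and is not an estimate. The conclusion rests on the definition.

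A reader might infer that the survival results are biased as well. They are not, as far as OS and PFS with documented progression are concerned. The matter should be settled before database lock, but it does not threaten the study's main results.

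**What to change.** Reconcile the synopsis endpoint section, Sections 3.3.1, 3.3.3 and 3.3.4, and footnote 2 of Table 1. State whether the SAP algorithm applies to all patients or only where progression is missing or poorly documented. For analysis, define:

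1. LOT n+1 starts at the first start date, on or after documented progression, of a new or changed regimen, or of a regimen restarted after having been stopped.
2. An unchanged LOT n or maintenance regimen that continues across progression stays in LOT n, flagged as treatment beyond progression, until LOT n+1 starts.
3. Agents carried over and given with the new regimen count in LOT n+1 from its start date.
4. Reintroduction of induction agents after progression is shown as its own category.

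Progression still gates the line, so the plan's declared choice is kept. The simpler rule, that a line opens only with an agent absent from the previous regimen and that all old agents stay in the old line, should be avoided. It would remove carried-over bevacizumab, or the 5-FU and leucovorin shared by FOLFOX and FOLFIRI, from a true second-line combination. It would also never open a line for a full regimen restarted after progression off treatment.

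The cost is a small amount of wording and programming, using agent names and start and stop dates already collected. It concerns classification in the analysis only, not how patients are treated.
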